8.4.5 Adverse Event Reporting

It is both the Principal Investigator's (PI) and the Sponsor's responsibility to ensure the safety of those on the clinical trial. The PI is responsible for tracking adverse events during the study and providing adverse events lists to the Sponsor at regular intervals per request. In addition, the PI is responsible for updating the Sponsor about known risks from the drug, as discovered from literature searches or other means. Adverse events will be reported in accordance with the NIH Office of Human Subjects Research Protection policy #801.

8.4.6 Serious Adverse Event Reporting

Following the subject's written consent to participate in the study, all SAEs, whether related or not related to study drug, must be collected, including those thought to be associated with protocol-specified procedures. All SAEs must be collected that occur within 30 days of discontinuation of dosing. The investigator should report any SAE that occurs after these time periods and that is believed to be related to study drug or protocol-specified procedure.

An SAE report should be completed for any event where doubt exists regarding its seriousness. If the investigator believes that an SAE is not related to study drug, but is potentially related to the conditions of the study (such as withdrawal of previous therapy or a complication of a study procedure), the relationship should be specified in the narrative section of the SAE Report Form.

SAEs, whether related or not related to study drug, (including pregnancies) must be reported to United BioSource Corporation (UBC) (a contract research organization contracted by Amryt Pharma) on an SAE Report Form or similar form (e.g. CIOMS, MedWatch) and submitted as soon as possible but not more than 7 calendar days in the event of a death or a life-threatening event or in 15 calendar days for all other SAEs. The SAE report(s) and are to be transmitted via email or confirmed facsimile (fax) transmission to:

SAE Email Address: [contact]

Abbreviated Title: Effects of leptin in insulin resistance

Version Date: AM N ver. (approved 10/21/20); rev for AM O (5/5/21)

If only limited information is initially available, follow-up reports are required. (Note: Follow-up SAE reports should include the same investigator term(s) initially reported). If an ongoing SAE changes in its intensity or relationship to study drug or if new information becomes available, a follow-up SAE report should be sent to the United BioSource Corporation (or designee) using the same procedure used for transmitting the initial SAE report. All SAEs should be followed to resolution or stabilization.

Per NIH HRPP SOP 801, all serious adverse events will be reported to the IRB at the time of annual review if they do not meet the expedited reporting criteria. The PI will report all deaths per the NIH HRPP SOP #801.

In accordance with the requirements of 21 CFR 312.32, the PI or designee will report all SAEs, whether or not these are considered related to the investigational drug or study intervention, that occur throughout the study to the Sponsor, including those events listed in the protocol or Investigator's Brochure as anticipated to occur, as follows:

Deaths: within 24 hours of the investigator's awareness

All other SAEs: within 48 hours of the investigator's awareness

All AEs will be sent to the Sponsor quarterly, or at minimum annually, for submission to the FDA in the IND Annual Report.

The PI will immediately report all deaths and SAEs to the Sponsor by disclosing all event-related information in a completed MedWatch Form 3500A. This form should include the IND number, protocol number, PI name, and an assessment on the reasonable possibility of a relationship between the event and the study drug or intervention. The completed MedWatch Form 3500A will be sent to the Clinical Director/CEO and/or designated medical monitor with a copy to the NIH Office of Research Support & Compliance (ORSC) Regulatory Support Section.

The CEO and/or designee will be responsible for determining whether the event is reportable to the FDA as an IND Safety Report if it is a serious, unexpected, and suspected adverse reaction (SUSAR). If the sponsor determines the SAE meets the criteria of a SUSAR, the ORSC will submit an Initial IND Safety Report to the FDA no later than 15 calendar days after the PI's notification of the event to the Sponsor. Deaths or life-threatening events will be reported to the FDA no later than 7 calendar days after the PI's notification of the event to the Sponsor. The Sponsor will submit any relevant additional information in a Follow-up IND Safety Report no later than 15 calendar days after receiving the information. All SAEs will be monitored until satisfactory resolution. All AEs and SAEs will be documented on appropriate study records.

8.4.7 Events of Special Interest

Overdose

An overdose is defined as the accidental or intentional administration of any dose of a product that is considered both excessive and medically important. All occurrences of overdose must be reported as an SAE.

Infectious agent transmission by investigational product

Abbreviated Title: Effects of leptin in insulin resistance

Version Date: AM N ver. (approved 10/21/20); rev for AM O (5/5/21)

Suspected transmission of an infectious agent (e.g., pathogenic or nonpathogenic) via the study drug is an SAE. Although overdose and cancer, are not always serious by regulatory definition, these events will be handled as SAEs (per Amryt Pharma request).

8.4.8 Reporting of Pregnancy

Should a patient become pregnant while on study, per 45 CFR 46.204, (1) no inducements, monetary or otherwise, will be offered to terminate a pregnancy, (2) individuals engaged in research will not be involved in any decisions as to timing, method, or procedures used to terminate a pregnancy, and (3) individuals engaged in the research will have no part in determining viability of a neonate.

Pregnancies will be recorded on a United BioSource Corporation (UBC) Pregnancy Surveillance Form. The investigator will notify the Amryt Pharma via UBC (a contract research organization contracted by Amryt Pharma) (or designee) Medical Monitor of confirmed pregnancies and forward the Pregnancy Surveillance Form to UBC (or designee) within 7 business days of the PI is first notified of the pregnancy. Follow-up information regarding the course of the pregnancy, including perinatal and neonatal outcome and, where applicable, offspring information will be reported on the Pregnancy Surveillance Form. Any pregnancy that occurs in a female partner of a male study participant should be reported to Amryt Pharma via UBC. Information on this pregnancy will be collected on the Pregnancy Surveillance Form. Forms are to be transmitted via email to:

Email address: [contact]

8.5 UNANTICIPATED PROBLEMS

8.5.1 Definition of Unanticipated Problems (UP)

Any incident, experience, or outcome that meets all of the following criteria:

- Unexpected in terms of nature, severity, or frequency given (a) the research procedures that are described in the protocol-related documents, such as the Institutional Review Board (IRB)-approved research protocol and informed consent document; and (b) the characteristics of the participant population being studied; and
- Related or possibly related to participation in the research (“possibly related” means there is a reasonable possibility that the incident, experience, or outcome may have been caused by the procedures involved in the research); and
- Suggests that the research places participants or others (which many include research staff, family members or other individuals not directly participating in the research) at a greater risk of harm (including physical, psychological, economic, or social harm) than was previously known or expected.

8.5.2 Unanticipated Problem Reporting

The investigator will report unanticipated problems (UPs) to the NIH Institutional Review Board (IRB) as per Policy #801.

8.5.3 NIH Intramural IRB Reporting of IND Safety Reports

Only IND Safety Reports that meet the definition of an unanticipated problem will need to be reported to the NIH Intramural IRB.

9 STATISTICAL CONSIDERATIONS

9.1 STATISTICAL HYPOTHESIS

- Primary Endpoint(s): The primary outcome measure is improvement in HbA1c after 1 year of metreleptin,
- Secondary Endpoint(s): A number of secondary endpoints will also be studied. These include fasting blood glucose, and insulin, and C-peptide levels, as well as the glucose, insulin, and C-peptide responses to glucose tolerance tests. In the pilot study, we have observed up to a 40% reduction in fasting blood glucose, and an even greater reduction in endogenous hyperinsulinemia. While we would hope to see changes of this magnitude we cannot pre-define the extent of improvement or lack thereof that may occur.
- Exploratory Endpoints: These include body weight, body composition, creatinine clearance, and urine 24-hour protein. In addition, we will include hypothalamic pituitary parameters, LH/FSH, and thyroid function.

9.2 SAMPLE SIZE DETERMINATION

Published data from 5 subjects who participated in this study [2] indicated the A1c change 6 months after treatment was about 2.1 with standard deviation of 1.4. Based on these data, a sample size of 6 will lead to a power of 80% (at a two-sided alpha of 0.05). A sample size of 7 would allow detection an A1c change of 2.0 with a standard deviation of 1.5.

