1.1 SYNOPSIS

Title:	Phase II Trial of Effect of Leptin Therapy in Severe Insulin Resistance
Study Description:	Patients with mutations of the insulin receptor have diabetes that is challenging to control with conventional therapies, leading to early morbidity and mortality. We hypothesize that recombinant leptin (metreleptin) in these patients will improve glycemia control.
Objectives:	Primary Objective : To determine if 1 year of metreleptin will improve glycemia control in patients with genetic defects of the insulin receptor. Secondary Objectives : To determine mechanisms by which metreleptin improves glycemia.
Endpoints:	Primary Endpoint : Hemoglobin A1c. Secondary Endpoints : fasting plasma glucose, fasting insulin/C-peptide, glucose/insulin/C-peptide area under the curve during oral glucose tolerance test.
Study Population:	20 male or female patients with mutations of the insulin receptor, age ≥ 5 years, at the NIH Clinical Center
Phase:	2
Description of Sites/Facilities	
Enrolling Participants:	NIH Clinical Center
Description of Study Intervention:	Open label study of metreleptin, 0.2 mg/kg/day (max dose 0.24 mg/kg/day).
Study Duration:	Indefinite as long as patients demonstrated benefit
Participant Duration:	12 months (may be extended if patient demonstrates benefit)

Abbreviated Title: Effects of leptin in insulin resistance

Version Date: AM N ver. (approved 10/21/20); rev for AM O (5/5/21)

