4 STUDY DESIGN

4.1 OVERALL DESIGN

This study is designed to investigate the effect of recombinant leptin on various metabolic and hormonal abnormalities in patients with known or suspected mutations of the insulin receptor gene. These patients have low leptin levels in addition to other metabolic abnormalities. This study utilizes an open-label design, and the accrual ceiling is set at 20 patients. Cumulative changes in each patient will be compared to his/her baseline state after 6 and 12 months. The primary outcome will be assessed after 12 months of study drug. After the patient has completed one year of therapy and has shown metabolic improvement on the medication and the patient desires to continue therapy, the PI at NIH will consider extending therapy on an annual basis. The study medication is supplied through Amryt Pharma, and neither NIH nor Amryt Pharma can guarantee its availability after the study ends.

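### Section 9.2 bases its 80% power at n=6 on the 6-month HbA1c change (2.1), but the primary endpoint is at 12 months, where the protocol's own means give 1.7

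*Combined protocol and SAP*

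**What the plan says.** The timing of the primary outcome is consistent across the protocol. The synopsis (1.1) gives the objective as "To determine if 1 year of metreleptin will improve glycemia control". Section 4.1 says "The primary outcome will be assessed after 12 months of study drug". Section 9.1 says "The primary outcome measure is improvement in HbA1c after 1 year of metreleptin".

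Section 9.2 uses a different time. It starts from "Published data from 5 subjects who participated in this study", reports that "the A1c change 6 months after treatment was about 2.1 with standard deviation of 1.4", and concludes that "a sample size of 6 will lead to a power of 80% (at a two-sided alpha of 0.05"). It then adds: "A sample size of 7 would allow detection an A1c change of 2.0 with a standard deviation of 1.5". That last sentence names no timepoint.

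Section 2.2 cites the same publication, also with five patients from this study. It gives mean HbA1c (SD) of 11.4 (1.1) at baseline, 9.3 (1.9) at 6 months and 9.7 (1.6) at 12 months. It prints P=0.007 after the 12-month value without naming the test.

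On numbers, section 4.1 states that "the accrual ceiling is set at 20 patients". Section 5.6 reports 11 enrolled and 20 anticipated. Section 9.3.2 restricts the efficacy analysis to participants who took at least 70% of the study drug, and the number expected to qualify is not given.

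**The concern.** The effect size in a sample-size statement should be the one expected for the primary endpoint at the time it is assessed. Here the 6-month change was used although the 12-month means for the same patients are in the protocol, and the 12-month change is smaller. No reason is given for letting 6-month data stand in. The n=7 sentence does not close the gap: even read as a general detectable change, its 2.0 is larger than 1.7.

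Section 9.2 is the plan's only sample-size justification. A reader would take from it that six or seven evaluable patients are enough for the 12-month test, and the plan has not established that.

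**Working it through.** **Method.** Section 9.4.1 makes each patient his or her own control and names the t-test, so I take a paired t-test, two-sided alpha 0.05. Power is P(|T| > t(0.975, n−1)), where T is noncentral t with n−1 degrees of freedom and noncentrality δ√n/σ. Here δ is the mean change and σ the SD of the within-patient change.

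**1. The plan's own figures.**
- 2.1, SD 1.4, n=6: noncentrality 2.1 × √6 / 1.4 = 3.67, critical value 2.571, power 83.3%. At n=5 it is 71.1%, so 6 is the smallest n that reaches 80%.
- 2.0, SD 1.5, n=7: noncentrality 2.0 × √7 / 1.5 = 3.53, critical value 2.447, power 83.4%. At n=6 it is 74.3%.

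Both statements reproduce.

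**2. Change at each time, from section 2.2.** 6 months: 11.4 − 9.3 = 2.1, which matches 9.2. 12 months: 11.4 − 9.7 = 1.7.

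**3. SD of the 12-month change.** It is not stated. From the SDs at baseline and 12 months, σ² = 1.1² + 1.6² − 2ρ(1.1)(1.6) = 3.77 − 3.52ρ, where ρ is the correlation between the two visits. The values considered are:
- *About 0.75.* If P=0.007 is a paired t-test of the 12-month change in five patients, then t = 5.096 on 4 degrees of freedom and σ = 1.7 × √5 / 5.096 = 0.746. The test is not stated, so this is conditional.
- *1.17.* The 6-month figures imply ρ = (1.1² + 1.9² − 1.4²) / (2 × 1.1 × 1.9) = 2.86 / 4.18 = 0.684. If that carries over, σ = √(3.77 − 3.52 × 0.684) = 1.167.
- *1.4 and 1.5.* The SDs used in 9.2, carried over to 12 months as an assumption.
- *1.9.* Needs ρ = (3.77 − 3.61) / 3.52 = 0.05, so it is a near-extreme case and deserves little weight.

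**4. Power for a change of 1.7.**

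| SD of change | n=6 | n=7 | n=8 | n=11 | n=20 |
|---|---|---|---|---|---|
| 0.75 | 99% | >99% | >99% | >99% | >99% |
| 1.17 | 81% | 89% | 94% | 99% | >99% |
| 1.4 | 66% | 76% | 84% | 95% | >99% |
| 1.5 | 61% | 71% | 78% | 92% | >99% |
| 1.9 | 43% | 51% | 59% | 76% | 97% |

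**5. Thresholds.** At n=6, 80% power needs a standardised change of 1.435, so the SD may be at most 1.7 / 1.435 = 1.185, or about 1.19. The smallest n for 80% is 6 at SD 1.17, 8 at SD 1.4 (84%), 9 at SD 1.5 (84%) and 12 at SD 1.9 (81%).

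**The case against.** The strongest reply is that the 12-month change may vary less between patients than the 6-month change, in which case n=6 is still enough. Two routes from the documents' own figures point that way. Carrying over the 6-month correlation gives SD 1.17 and 81% power. Reading P=0.007 as a paired t-test at 12 months gives SD about 0.75 and 99% power. On that reading SD 1.4 would not fit: t = 1.7 / (1.4 / √5) = 2.72 on 4 degrees of freedom gives P of about 0.053. This stands as a reason not to assert a shortfall. It does not rescue 9.2, because the plan makes no such argument, gives no 12-month SD and does not name the test, and the P value may come from an overall test across visits.

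The second reply is that nothing depends on six patients: 11 are enrolled, the ceiling is 20, and no section stops accrual at 6 or 7. That also stands, and it limits the point to the stated justification. But 9.2 gives no power for 11 or 20.

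A reader might infer more: that the trial is underpowered, or that power at n=6 is really 66%. The documents support neither. The 66% holds only if the 6-month SD of 1.4 applies at 12 months, and at the numbers enrolled and anticipated, power for 1.7 is high at every SD considered except 1.9 with 11 patients (76%). Nor do the documents show that 6 months was chosen because its change was larger; they give no reason at all.

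**Conclusion.** The point holds as a mismatch of timepoint in the sample-size justification. The calculation in 9.2 is right for its inputs, but the inputs belong to 6 months and the primary endpoint to 12, where the protocol's means give 1.7 and not 2.1. Whether n=6 suffices depends on an SD that the documents do not give. Power ranges from 99% (SD 0.75) through 81% (1.17) to 66% and 61% (1.4 and 1.5), with 43% at the near-extreme 1.9. A shortfall at n=6 is therefore possible but not shown, and the trial is not shown to be underpowered.

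This rests on a paired t-test and on the same five patients contributing at baseline and 12 months, so that the difference in means equals the mean change. The 1.7 is itself imprecise: with five patients its standard error would be 1.4 / √5 = 0.63 if the SD is 1.4. The 95% at 11 and over 99% at 20 (SD 1.4) assume that all those patients are evaluable under the 70% rule. Severity: minor.

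**What to change.** Rewrite section 9.2 for the 12-month change of 1.7, using that change's own paired SD. The five patients took part in this study, so the sponsor can calculate it from their data. Alternatively, keep the 6-month figures and say why they stand in for 12 months.

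Replace the n=6 and n=7 sentences with power at the number of patients expected to be evaluable (for example 8, 11 and 20), over an SD range of about 0.75 to 1.9. Mark the low end as conditional on how P=0.007 was obtained and the high end as near-extreme. If the published P value is relied on, name the test behind it.

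The cost is one paragraph. The stated minimum n may look less favourable (8 at SD 1.4, 9 at SD 1.5). No extra patients are needed: at the ceiling of 20, power for 1.7 is 97% or more across that whole range if all are evaluable.

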9.3 POPULATIONS FOR ANALYSES

9.3.1 Evaluable for toxicity

All participants will be evaluable for toxicity from the time of their first treatment with metreleptin.

9.3.2 Evaluable for objective response

Data will be analyzed as Per-Protocol Analysis Dataset: including the subset of the participants who took at least 70% of study intervention.

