1.2 SCHEMA

1.3 SCHEDULE OF ACTIVITIES (SOA)

Baseline Visit (3-4 days): Patients will be admitted to the research center.

They will have their history and physical examination completed on the day of admission. Following a 12 hour fast, the OGTT will be performed. In addition, patients' capillary blood glucose will be measured before each meal and at bedtime. 24-hour glucosuria (and other 24 hour urine studies) will also be determined. After baseline testing has completed, patients will be trained in the proper storage, preparation, and administration of metreleptin injection, and will begin metreleptin injections subcutaneously during the hospitalization. Therapy will begin at determined efficacious dose for this group of patients of (0.2 mg/kg/day for male and female patients). For patients who reside outside the US, sufficient drug supply will be sent home with the patient to last until the next scheduled visit. For patients who reside within the US, a 3 month supply of drug will either be sent home with the patient or shipped to the patient's home.

Months 6 and 12 and every 6 months thereafter (3-4 days): At the end of 6 months, patients will return to the Clinical Center for collection of the same data obtained at baseline. For patients for whom it is challenging to travel to the Clinical Center every 6 months (i.e. ex-US patients), visits may be conducted every 12 months after the first year per investigator discretion. In the event that circumstances beyond our control preclude the travel of one or more of the study participants to the NIH Clinical Center for a visit, or otherwise would put their health at greater risk (i.e. epidemic or pandemic), we will endeavor to establish capabilities for remote visits. Specifically, the study team will request local laboratory studies to be done, to include, at a minimum, basic chemistry panel, CBC with diff, hemoglobin A1c, and pregnancy testing in female subjects with reproductive capacity, and conduct a telehealth/telephone visit with the patient. Telehealth/telephone visits will adhere to HHS guidance (<https://www.hhs.gov/hipaa/for-professionals/special-topics/emergency-preparedness/notification-enforcement-discretion-telehealth/index.html>) and can use all telehealth modalities under the good faith provision during a pandemic/epidemic as allowed by HHS for care of study participants.

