6.4 STUDY INTERVENTION COMPLIANCE

Adherence to study drug will be assessed by frequency of medication refill requests as well as documentation of medication use in the medical record.

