7 STUDY INTERVENTION DISCONTINUATION AND PARTICIPANT DISCONTINUATION/WITHDRAWAL

7.1 DISCONTINUATION OF STUDY INTERVENTION

See section 7.2

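### The only efficacy dataset is the subset who took at least 70% of drug; an all-treated month-12 HbA1c analysis should be reported beside it

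*Combined protocol and SAP*

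**What the plan says.** Section 9.3 defines two populations. For efficacy, section 9.3.2 says: "Data will be analyzed as Per-Protocol Analysis Dataset: including the subset of the participants who took at least 70% of study intervention". For safety, section 9.3.1 says: "All participants will be evaluable for toxicity from the time of their first treatment with metreleptin". No all-treated efficacy set appears, either as the main analysis or as a sensitivity analysis.

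The endpoint is on-drug and at one year. Section 9.1: "The primary outcome measure is improvement in HbA1c after 1 year of metreleptin". Section 4.1: "The primary outcome will be assessed after 12 months of study drug". Adherence is measured under section 6.4: "Adherence to study drug will be assessed by frequency of medication refill requests as well as documentation of medication use in the medical record".

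Section 7.1, on stopping the drug, reads in full "See section 7.2", and section 7.2 concerns leaving the study. Its reasons include adverse events, failure to comply with self-monitoring and visits, and metreleptin losing its effect. No HbA1c is required after the drug is stopped. Sections 9.4.1 to 9.4.3 name t-tests, ANOVA and log-transformation, and state no handling for an absent month-12 value.

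**The concern.** The 70% rule selects on something that happens after baseline. A participant who stops because the drug is not working, or is not tolerated, can fall below 70%, can have no month-12 value, or both. Either way that person leaves the primary analysis for a reason that may be linked to the outcome.

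The primary claim is a mean within-patient change with each participant as their own control. No comparison arm loses participants by the same route, so the selection feeds straight into the estimate. Section 2.2 reports that the improvement in the two pilot patients had gone three months after the drug was withdrawn. Those left out would therefore be expected to have smaller falls at month 12 than those kept in. At stake is whether the reported figure can be read as the effect of starting metreleptin or only as the effect in those who continued it.

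**Working it through.** **Step 1. The plan's own figures.** Section 9.2 gives N = 6 for a change of 2.1 (SD 1.4) and N = 7 for a change of 2.0 (SD 1.5), with 80% power at two-sided alpha 0.05. A paired t-test, using the noncentral t distribution with noncentrality (change/SD) × √N, gives:

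- 2.1 / 1.4: 71.1% at N = 5 and 83.3% at N = 6, so the smallest N is 6.
- 2.0 / 1.5: 74.3% at N = 6 and 83.4% at N = 7, so the smallest N is 7.

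Both sample sizes reproduce. Neither allows for exclusions.

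**Step 2. Inputs for the illustration.**

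- Fall in those retained: 11.4 − 9.7 = 1.7 points (12-month means in five participants, section 2.2).
- N = 20 (accrual ceiling, section 4.1).
- Number excluded: 1 or 2. This is an assumption, as the documents give no rate.
- Share r of the benefit kept by those excluded: 0 or 0.5. This is also an assumption.

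**Step 3. All-treated mean fall** = [(20 − k) × 1.7 + k × r × 1.7] / 20, where k is the number excluded.

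| k | r | All-treated fall | Overstatement by 1.70 |
|---|---|---|---|
| 1 | 0.5 | (32.3 + 0.85)/20 = 1.658 | 0.04 (2.6%) |
| 1 | 0 | 32.3/20 = 1.615 | 0.085 (5.3%) |
| 2 | 0.5 | (30.6 + 1.7)/20 = 1.615 | 0.085 (5.3%) |
| 2 | 0 | 30.6/20 = 1.53 | 0.17 (11.1%) |

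With k = 0 the difference is nil.

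**Step 4. Reverse case.** Suppose those excluded had fallen by 2.1, the 6-month figure. The all-treated fall is then (32.3 + 2.1)/20 = 1.72 for one, or (30.6 + 4.2)/20 = 1.74 for two. Here 1.70 understates by 1.2% or 2.3%.

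**Step 5. Effect of the 70% period.** 70% of 12 months is 0.70 × 12 = 8.4 months. Someone who takes every dose and stops at month 7 has 7/12 = 58% of the year and is excluded. Someone who stops at month 9 has 9/12 = 75% and is included, but may have no month-12 HbA1c. For early stoppers, then, the missing value matters as much as the threshold.

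**Step 6. Power of an all-treated analysis.** Assumptions: a 1.7-point fall in continuers, the 6-month planning SDs of 1.4 / 1.5 carried over to month 12, and a two-sided t-test at 0.05.

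- N = 20, 10% with zero mean change, SD 1.4: mean 0.9 × 1.7 = 1.53, SD √(1.4² + 0.1 × 0.9 × 1.7²) = 1.49, power 99.2%.
- N = 11 (currently enrolled, section 5.6), no stoppers: 95.1% / 92.2%.
- N = 11, two stoppers varying around zero with the same SD: about 78% / 73% by simulation. A noncentral-t approximation gives 76.7% / 71.9%.
- N = 11, two stoppers set to exactly zero: 88.3% / 83.6%. The gap from the previous line arises because a fixed zero removes variance that real off-drug values would have.

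**The case against.** The endpoint is worded as change on metreleptin, so an on-drug analysis is a legitimate choice, and section 9.4.9 says the trial is not registrational. The illustrated bias, at most 0.17 points, is smaller than the standard error at N = 20 (1.4/√20 = 0.31 to 1.5/√20 = 0.34). All of this stands. It limits the weight of the point but does not explain why the on-drug result should be the only one.

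The documents also reduce missing data. Section 1.3 provides for local HbA1c tests and accepts outside laboratory results for efficacy, and section 7.3 has missed visits rescheduled within six months. These are collection measures. They do not require a value after stopping or say how an absent one is analysed. Section 9.4.1 refers to the analysis used in a lipodystrophy study. That method is not reproduced here, so one can say only that no missing-value rule is stated in these documents. Section 9.4.1 also says that all patients are analysed against baseline. In context this describes the own-control comparison and does not define a population.

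Two stronger readings are tempting.

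- A reader might infer that the 70% has no usable period, because the synopsis gives study duration as "Indefinite as long as patients demonstrated benefit", so that an early stopper could count as fully adherent. The documents do not support that. The synopsis sets participant duration at 12 months in the first instance, and sections 4.1 and 9.1 put the primary outcome at one year. The missing denominator is a detail to write down.
- A reader might infer from the 3-month and visit-to-visit drug supplies that someone stopping at month 7 would pass on refills alone. Section 6.4 also uses the medical record of medication use, so refills alone are not the plan's measure.

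**Conclusion.** The point holds as a cheap improvement that should be made. Following the plan as written, the primary HbA1c result comes only from participants selected on drug taken after baseline, and the listed withdrawal reasons allow that selection to follow outcome.

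Overstatement is the likelier direction. This rests on the loss of benefit after withdrawal in two pilot patients and reverses if good responders stop for other reasons. The illustrated size is 0.04 to 0.17 points (3 to 11%) at N = 20 with one or two excluded, and zero with none. The number excluded and the benefit they keep are assumptions. The neutralizing-antibody frequency in section 2.3.1 should not be used in their place, since it is not a stopping rate.

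A reader might go further and conclude that the trial is underpowered or its primary analysis invalid. The documents do not support that. The stated sample sizes reproduce, and an on-drug estimate is valid if it is labelled as one.

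**What to change.** 1. Add to section 9.3.2 an all-treated efficacy set: *all participants with at least one dose of metreleptin and a baseline HbA1c*. Report the month-12 HbA1c change in this set alongside the 70% set, and label the latter as on-drug. Which of the two is the headline is partly a matter of judgement.
2. In section 7 and the schedule, state that a month-12 HbA1c will be sought, with the participant's agreement, from anyone who stops drug before month 12. Use the outside-laboratory provision in section 1.3 and the rescheduling in section 7.3. Record any change in other glucose-lowering therapy with the value, because it affects interpretation.
3. Pre-state how a still-missing month-12 value is handled, with sensitivity analyses that keep its uncertainty, for example off-drug values varying around baseline, and the month-6 on-drug value where available. A fixed change of zero should not be the only rule. It understates variance, and it is not conservative if HbA1c rises above baseline off drug.
4. As a clarification, define the 70% as drug taken divided by drug due from baseline to month 12, with time after stopping counted as not taken. Date this definition, since 12-month results for five participants are already published.

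**Cost.** This needs wording in sections 7 and 9, a schedule line and a few outside HbA1c tests. The headline change may be slightly smaller. Power is somewhat lower: about 78% / 73% (SD 1.4 / 1.5) in the N = 11 case with two stoppers. Some values for the 11 already enrolled may not be recoverable.
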